- v. **Kidney Functioning.** We will use eGFR to measure kidney function using the abbreviated Modification of Diet in Renal Disease study equation as is recommended.^{41,42} Thus, we will measure serum creatinine from a baseline blood draw. Along with age, gender, and race, this information will be used in an online GFR calculator that is made available by the National Kidney Disease Education Program. At baseline, participants will provide a urine specimen so that we can determine the protein/creatinine ratio.⁴²
- vi. **Covariates.** Covariates to be assessed include behavioral factors (e.g., smoking, alcohol use, unhealthy diet, physical activity), socio-economic factors (e.g., health insurance status, income, and education), psychosocial factors (e.g., depression, quality of life), comorbidities (e.g., health conditions, medications, blood glucose control measured via HbA1C, and ApoL1 status), and demographics such as age, sex, and body mass index. Depressive symptoms will be assessed with the Beck Depression Inventory (BDI),⁶⁰ which is a self-administered 21-item scale that has acceptable sensitivity and specificity with regards to a clinical diagnosis of depression, and also provides a continuous measure of depressive symptoms. We will also assess previous self-reported diagnosis of major depression and previous use of antidepressant medications in addition to kidney disease quality of life.⁶¹
- vii. **Acute vs. Discriminatory Stress Experimental Manipulation.** At the end of the rest period, patients will be asked to recall a personally relevant stressor, involving a general or racism-related stressful experience. Participants will be randomized into one of the two recall groups. In the general stress protocol, participants will be asked to give a detailed account of a stressful experience (non-racial in nature) in which they felt so upset, angry, or annoyed at the time that talking about it during the clinic visit might still be upsetting to them. In the racism recall protocol, patients will be asked to provide a detailed account of a stressful experience involving *racism*-- one where they were so upset/angry/annoyed at the time that talking about it during their visit might still be upsetting to them. In both scenarios, patients will be asked to visualize the situation and recall the details of what happened, including: 1) where they were; 2) who else was there; 3) what was said and done (by the participant and by any other individuals present

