The first hypothesis is a meditational hypothesis. We recognize that Baron and Kenny⁶⁴ methods for testing mediation are among the most widely cited, but also acknowledge that there are convincing critiques of this approach such as the requirement that there be a significant direct effect of the independent variable on the outcome in order to proceed with meditational analyses.^{65,66} Thus, we will use meditational methods proposed by Zhao et al⁶⁵ that entail first running the Preacher and Hayes⁶⁷ SPSS syntax commands to generate “bootstrap” results for the indirect effect of chronic discriminatory stress (controlling for general stress) on each of the two kidney outcomes (eGFR and proteinuria) through the inflammatory pathway as measured by each of the proposed biomarkers (MCP-1, IL-6, suPAR). Bootstrapping relaxes assumptions about the shape of the sampling distribution of the indirect effect over repeated sampling from the population.⁶⁸ These analyses will control for relevant covariates. Next we will classify the type of mediation using the Zhao et al typology (complementary, competitive, indirect only, direct only, or non-mediation), and proceed with interpreting the findings in light of our hypotheses. We will consider using structural equation modeling as another technique recommended to test mediation.^{69,70}

The second hypothesis will entail use of a 2X3 ANOVA to simultaneously test the main effects of stress recall (race-related or not) (discriminatory stress vs. general stress) and data collection time point (rest, stress, and recovery) on each of the outcomes (i.e., each inflammatory biomarker and blood pressure), also controlling for the relevant covariates. This test provides a form of economy by examining multiple effects at a time, while also allowing us to study the interaction between study condition and time.⁷¹

C. Statistical Power

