The proposed proof-of-concept study is designed to generate effect sizes to inform a future power analysis and thereby establish the legitimacy of studying this topic in a subsequent large-scale clinical trial. Thus, it is not intended to achieve the level of power to demonstrate statistical significance as is common in larger studies. Nevertheless, regarding study aim 1, if we were to perform a multiple regression with 8 predictors that explain just 15% of the variance in a given outcome, we would achieve 84% power at $\alpha=.05$ (<http://danielsoper.com/statcalc3/calc.aspx?id=9>) at N=100. For aim 2, collecting data at multiple time points is one way to maximize power. If we just consider the two study groups (intervention and control) we would achieve power of .80 to detect a medium effect (.25) at $\alpha=.05$ with a sample of just 64 participants.⁷²

IX. Training of study team

All research staff maintains a current CITI, (Group 3 Social/Behavioral) certification. Proof of certifications has been uploaded for further review. Corresponding study team members (including members of the Georgia CTSA team and nurses within the Emory University Healthcare Nephrology clinic) will undergo study-specific training.

X. Plans for monitoring the study for safety

The Data and Safety Monitoring Plan (DSMP) outlined below will adhere to the protocol approved by Emory University. An IRB-approved written informed consent will be obtained from each participant at entry into the study; elements of informed consent will include: (a) having the participant review the study consent form; (b) having the investigator(s) or study staff meet with the participant to review the consent, confirm understanding, and answer any questions; and (c) once the investigator(s) or study staff are convinced that the protocol is understood and that there is agreement to participate, having the consent signed. The principal investigator (PI) will review all data collection documents weekly for completeness and accuracy of the data as well as protocol compliance. The PI will review this protocol on a continuing basis for participant safety and include the results of the review in annual progress reports submitted to the IRB and the NIH.

Patient Monitoring will be performed by the P.I., Co-Investigators, the Project Coordinator and medical staff present during the experimental manipulation. Also, H&P is required per the GCTSA protocol.

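### The 84% power quoted for Aim 1 is for an omnibus R-squared test the plan does not run; no power or precision is given for the planned bootstrap indirect effect

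*Combined protocol and SAP*

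**What the plan says.** Section VIII.C (Statistical Power) first limits its own claim. The study is a proof of concept meant to yield effect sizes, and "it is not intended to achieve the level of power to demonstrate statistical significance as is common in larger studies". It then turns to Aim 1 and offers a hypothetical calculation at alpha .05 and N=100: "multiple regression with 8 predictors that explain just 15% of the variance in a given outcome, we would achieve 84% power".

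Section VIII.B (Main Outcome Analyses) describes the analysis that will be done: "The first hypothesis is a meditational hypothesis". The plan is to generate bootstrap "results for the indirect effect of chronic discriminatory stress (controlling for general stress") on eGFR and on proteinuria, "through the inflammatory pathway as measured by each of the proposed biomarkers (MCP-1, IL-6, suPAR"). The models also adjust for relevant covariates, without saying how many. The result is then classified by a mediation typology, with structural equation modelling as an option. No analysis section names a test that a set of predictors jointly explains no variance.

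Section III.E, item vi, lists what may be adjusted for: "Covariates to be assessed include behavioral factors (e.g., smoking, alcohol use, unhealthy diet, physical activity"), followed by socio-economic, psychosocial, comorbidity and demographic items.

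**The concern.** Power belongs to a particular test of a particular hypothesis. The 84% answers whether any of eight predictors is related to the outcome. Hypothesis 1 asks whether one exposure, net of other stressors, acts on kidney function through a mediator.

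The omnibus test can reject with no stress effect at all. Item v of section III.E computes eGFR from creatinine together with age, gender and race, and item vi lists age and sex as covariates. Variables built into the outcome formula can therefore supply explained variance by themselves.

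What is at stake is interpretation. The only figure attached to Aim 1 is reassuring, and it says nothing about how often the planned analysis would detect an indirect effect or how precisely it would estimate one. Without that, a null mediation result could be read as more informative than it is.

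**Working it through.** **Inputs from the documents.** N = 100, alpha = .05, 8 predictors, R² = .15 (VIII.C); bootstrap indirect effect, 3 biomarkers × 2 outcomes = 6 such effects (VIII.B); candidate covariates (III.E, item vi).

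**Inputs not in the documents, hence assumed.** The standardised paths a (stress to mediator) and b (mediator to kidney outcome); the number of control variables; the type of bootstrap interval.

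**Step 1: reproduce the plan's figure.** Omnibus F test of R² = 0:
- f² = .15/.85 = .1765
- λ = N × f² = 17.65
- degrees of freedom 8 and 100 − 8 − 1 = 91
- power from the noncentral F = 83.6%, which matches the stated 84%.

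**Step 2: what the same 15% implies for one path.** This illustration uses the plan's own R². If the mediator uniquely holds a share s of the outcome variance, the one-degree-of-freedom test of its path has λ = 100 × s/.85. The splits are arbitrary and show only the range.
- s = .15/8 = .01875: λ = 2.21, power 31%
- s = .05: λ = 5.88, power 67%
- s = .076, about half of the 15%: λ = 8.9, power 84%

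By joint significance, both paths must be detected, so each figure is a ceiling on power for the indirect effect, however strong path a is.

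**Step 3: power for the planned kind of test.** Simulation at N = 100 of a 95% percentile-bootstrap interval for a × b, with paths equal and a control variable correlated .4 with the exposure. The 16-control column reflects the items named in item vi: 4 behavioural, 3 socio-economic, 2 psychosocial, 4 comorbidity and 3 demographic (4 + 3 + 2 + 4 + 3 = 16).

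| Both paths | 1 control | 16 controls |
|---|---|---|
| .14 | 7% | 3% |
| .26 | 43% | 31% |
| .30 | 65% | 46% |
| .345 | 79% | 67% |
| .39 | 92% | 84% |

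These are for a single indirect effect, with no adjustment for the six. Separate runs differ by a few points; at .345, for example, another run gave 83% and 71%.

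**Step 4: sensitivity to the interval type.** In a run with 8 predictors in the outcome model, percentile versus bias-corrected power was 4% versus 9% at .14, 45% versus 57% at .26, 62% versus 71% at .30 and 92% versus 94% at .39. A joint-significance approximation, which multiplies the power of the two path tests at a given partial correlation, gives .759 × .759 = 58% at .26 and reaches 80% at about .31 on both paths.

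**The case against.** The strongest defence is that VIII.C already disclaims power for significance, words the 84% as a supposition and names the test it refers to. That is true and limits the seriousness. It does not make the figure relevant: the sentence is explicitly about Aim 1, and the test that Aim 1 will use has no figure at all.

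A second objection is that any statement about indirect-effect power rests on path sizes the documents do not supply. This also stands. With both paths at .39, power is 92% with one control and 84% with sixteen, so the planned test does as well as the quoted figure or better. The table is a range, not an estimate of this study's power.

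Three stronger readings are tempting and should not be drawn.
- A reader might infer that the follow-on study would be planned on an overstated basis. Sections II and VIII.C say it will be planned from the observed effect sizes, and the 84% is not an input. Nor is N = 100 derived from it: section III.D sets quotas of 20 in each of five groups.
- A reader might infer that the planned model certainly has more than 8 terms. Item vi lists covariates to be assessed, whereas VIII.B adjusts only for relevant ones, and the number is left open.
- A reader might infer that omnibus power must fall as covariates are added. At a fixed R² of .15 it does, to 67% with 16 predictors and 60% with 20. But added covariates may raise R², and with 20 predictors an R² of about .21 restores 84%.

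**Conclusion.** The mismatch is established from the text: the 84% is correct for an omnibus R-squared test that the plan does not run, and the planned bootstrap indirect effect has no stated power or precision.

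The size of the gap is conditional. With both paths between .14 and .30, power for one indirect effect is well below 84%: about 7% to 65% with one control variable and 3% to 46% with sixteen. It approaches or passes 84% only when both paths are large, above about .345 with one control and at about .39 with sixteen. These figures assume equal paths, a percentile interval, complete data on 100 participants and no multiplicity adjustment. Bias-corrected intervals would raise them somewhat.

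Given the disclaimer and the conditional wording, this is a reporting fault in the power section. It is not a flaw in the sample size or the analysis method.

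**What to change.** In VIII.C, either delete the 84% or label it as power for an omnibus R-squared test with 8 predictors that does not refer to hypothesis 1.

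Add a short statement for the planned test: power, or expected confidence-interval width, for one indirect effect at N = 100. It should cover a range of path sizes and at least two covariate counts and say which bootstrap interval is used (percentile or bias-corrected). Expected interval width suits the stated purpose of generating effect sizes particularly well. A single value would be unsafe: at paths of .345 the answer is about 79% with one control and 67% with sixteen, so the assumptions must stand beside the numbers.

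The cost is wording only, with no change to sample size, procedures or data collection. The figure shown for Aim 1 becomes less favourable unless both paths are assumed to be large.

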Study participation entails completion of a computer administered personal interview (CAPI) that assesses experiences of general and discriminatory stress, behavioral and socio-economic variables, and other psychological characteristics. Upon completion of the CAPI, participants would be scheduled to attend a second session. During this session the experimental manipulation entails them being asked to recall a general or discriminatory stressor (the participant is randomized to one of the two groups), while changes in blood pressure and inflammatory processes are monitored. Finally, participants provide blood pressure assessments over a 24-hour period using an ambulatory blood pressure monitor (ABPM). These methods are described below.

Data Collection Procedures

Day 1: Consent, CAPI and 24-hour Ambulatory Blood Pressure Monitor (ABPM)

Day 1 of data collection will occur at the Nephrology clinic within the Emory University Hospital, Midtown location. Those who consent to participate in the study will first complete a CAPI in a small private room at the clinic immediately following their appointment. This is a self-administered survey in which responses are directly entered into an iPad at the time of administration, thereby eliminating the need for subsequent data entry. REDCap software will be used to securely collect and manage CAPI-questionnaire data. The key advantages of this method include allowing the interviewer to answer respondent questions, probe for adequate

answers, and accurately follow complex instructions or skip patterns.³¹ The survey will assess participants' experiences of general and discriminatory stress, behavioral and socio-economic variables, and other psychological characteristics. Participants will be paid a portion of the monetary incentive (\$50) at the conclusion of the survey interview. The proposed CAPI-questionnaire is attached.

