Next, participants will undergo a moderate psychological stress adapted from the commonly used Trier Social Stress Test (TSST)³³. The TSST protocol has been adapted for use in recalling race-related experiences³⁴ underscoring its appropriateness for our protocol. [name] (Co-Investigator) and colleagues, have also used a similar experimental protocol and will provide related expertise for this project.^{35,36} Participants will be asked to recount one real-life stressful situations; one event will be a stressful race-related event and one event will be a stressful event that is not race-related. We will randomize participants such that half will recall the racial experience and half will recall the non-racialized stressful event. Each participant will have an equal chance of being placed in the racialized or non-racialized experience group. The Project Coordinator will provide instructions using a script. Participants will be given two minutes to prepare their statement, and three minutes to deliver the statement. There will be an 'audience' present at each participant's speaking task. Aligning with previously conducted involving audiences^{33,35-38}, each audience will include two observers who are of same race as the participant (African American), to heighten stress responses. Observers will wear white coats, and will be trained on the study protocol such that their behaviors are identical for each

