manipulation task. The audience will be trained to remain neutral during the task, told to not show empathy and not to smile at any time during the test. Observers have not yet been identified, however once determined, the individuals serving as observers will obtain a CITI certification, and study staff will submit observer credentialing as amendment modification to the protocol. The project coordinator will also remain in the room while participants recall each designated stressful experience. Blood pressure readings will be taken every 1 minute during the participant's preparation time and the actual recall task. The participant will be expected to use the entire three minutes for recall in each exercise; the project coordinator will cue the participant to continue until the 3-minute mark via standardized prompts from a script. Participants will be asked to rate their level of distress caused by the stressful event using an adapted version of Cooper's racism recall scale.³⁴ and again rate their level of distress on a linear scale (0 to 100) using the SUDS³². Participants will undergo a 45-minute recovery period after the first recall task; blood pressure readings will be taken every 5 minutes during this period. Immediately following the first 45-minutes of recovery, participants will provide a third blood draw (6 mL). Participants will undergo another 45-minutes of recovery, and provide and one final blood draw (6 mL) at the conclusion of the recovery period.

Over the course of the study, participants will provide 3, 4 mL samples of blood and 3, 6mL samples of blood. A total of up to 30 mL may be taken over the course of the study. The project coordinator will debrief participants on the purpose of the experimental manipulation and common reactions to it. Participants will also be debriefed on the entire experimental manipulation experience, including the audience's purpose. Participants will be paid \$150 at the conclusion of Day 2 (\$50 for return of ABPM and \$100 for completion of experimental manipulation). The experimental protocol along with data time points are outlined in Figure 2.

Data Sources

Participants will be asked to provide data from the following sources:

- **Cross-sectional survey data** that are provided by completing the CAPI (see attached)
- **Medical chart data**, used only to verify their last eGFR in order to achieve equal numbers of participants by study stage/CKD diagnosis

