We will start by creating a data set that merges the survey data with all biometric data. Traditional data entry for the survey data will be unnecessary as data will be imported directly into SPSS from the REDCap software that houses the CAPI-questionnaire. Data will be cleaned, coded, and examined for any missing data or unlikely values. We will examine frequency distributions for all variables, with particular attention to variable ranges, missing values, and transforming variables as needed, depending on evidence of internal consistency within scales. Next, we will conduct exploratory analyses to determine whether participants with the different sequences (i.e. race-related recall first or second) differ on demographic, clinical, or behavioral variables. Specifically, we will use logistic models to regress recall sequence on all relevant variables. If significant differences are identified, we will conduct further analyses by stratifying by these particular variables and consider adjustment for these variables in our main analyses as described below.

B. Main Outcome Analyses

These analyses are driven by the two hypotheses stated above: (1) Chronic discriminatory stressors will be associated with poor kidney functioning independent of other chronic stressors

as mediated by CKD-related inflammatory biomarkers and autonomic arousal; (2) Discriminatory stressors will be more physiologically impactful than general stressors on critical CKD-related inflammatory biomarkers and blood pressure reactivity.

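### The Aim 2 power statement is wrong as written: 64 participants in total give about 50% power for the stated effect, not 80%

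*Combined protocol and SAP*

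**What the plan says.** Section VIII.C (Statistical Power) opens with a disclaimer. The study is meant to produce effect sizes for a later trial, and "it is not intended to achieve the level of power to demonstrate statistical significance as is common in larger studies". It then offers one power figure for each aim. The Aim 2 figure is: "If we just consider the two study groups (intervention and control) we would achieve power of .80 to detect a medium effect (.25) at" alpha .05 "with a sample of just 64 participants". A general power primer is cited as the source. The index behind .25, the sidedness, and whether 64 is a total or a per-group number are not stated.

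The Aim 2 comparison is between two parallel groups. The Data Collection Overview in Section III.E says "the participant is randomized to one of the two groups". The Day 2 procedures say "We will randomize participants such that half will recall the racial experience and half will recall the non-racialized stressful event". Item vii of the research instruments says "Participants will be randomized into one of the two recall groups". Planned enrolment is 100, filled by quotas of 20 in each of five kidney-function categories (Section III.D).

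**The concern.** The sentence sets the repeated measurements aside and speaks of a number of participants, not a number per group. A reader will take it that 64 people in total are enough and that 100 leaves a margin of 36. For a medium effect in a plain two-group comparison, 64 is the familiar number per group, so a total of 64 looked too small by half.

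This is the only power figure given for Aim 2. The two-group case is relevant because blood pressure reactivity is defined as one change score per participant (Section III.E, item viii). The study also exists to inform the sample size of a larger one, so a total that is half the required number could be carried forward.

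**Working it through.** **Inputs from the plan.** Alpha .05, effect .25 labelled medium, stated power .80 and 64 participants (Section VIII.C); half of the participants in each recall group (Section III.E); planned total 100.

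**Assumptions, because the plan is silent.** .25 is Cohen's f, which for two equal groups means d = 2f = .50. The test is two-sided, as an ANOVA F test of two groups is.

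**Formula.** Power = P(F′ > F crit), where F′ is noncentral F with df = (1, N − 2) and noncentrality λ = f²N. With f² = .0625:

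| Total N | Per group | λ = .0625 × N | F crit | Power |
|---|---|---|---|---|
| 64 | 32 | 4.00 | 3.996 | .504 |
| 100 (planned) | 50 | 6.25 | 3.938 | .697 |
| 126 | 63 | 7.875 | 3.918 | .795 |
| 128 | 64 | 8.00 | 3.916 | .801 |

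The two-sided noncentral t with d = .50 gives the same values.

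**Reproducing the plan's figure.** Under these assumptions .80 appears at 64 per group, 128 in total. It does not appear at 64 in total, where the stated power is about 30 points too high. The Aim 1 figure in the same section does reproduce: 8 predictors, R² = .15, N = 100, λ = 100 × .15/.85 = 17.65, df (8, 91), power .836 against the stated 84%. So the Aim 2 gap is not a general difference in method.

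**Other readings at 64 in total.**

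| Reading | Power |
|---|---|
| f = .25, one-sided | .631 |
| .25 is d | .166 |
| .25 is r (f = .258) | .529 |
| .25 is f-squared (f = .50) | .976 |
| .25 is eta-squared | .995 |

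None gives .80. One-sided at N = 100 gives .799, and 102 are needed to pass .80 (.806).

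**Detectable effect at 80% power, two-sided.** N = 64: f = .356 (d = .71). N = 100: f = .283 (d = .57).

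**Where the 64 might come from.** The plan does not say. Two explanations fit numerically:

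- A per-group number was written as a total (.801).
- The number belongs to a design in which each person does both recalls. A paired test with 64 people and d = .50 on the single-measurement SD has power .795 if the two responses are uncorrelated (.835 at a correlation of .1, .914 at .3). Traces of such a design remain: Section III.E, Day 2, has "Participants will undergo a 45-minute recovery period after the first recall task", and Section VIII.A compares "participants with the different sequences (i.e. race-related recall first or second".

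Neither supports the sentence, because each participant is now randomised to one recall.

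**The case against.** The strongest objection is that the sentence decides nothing. It follows an explicit statement that the study is not powered for significance, and the 100 come from quotas, not from the 64. That stands, and it limits the importance of the point. It does not make the number right: the figures are offered as reassurance despite the disclaimer.

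A second objection is that the sentence just before the claim says repeated measurement raises power, and the planned test is a 2x3 ANOVA with covariates (Section VIII.B). If the group effect is averaged over three time points, with λ = 3f²N/(1 + 2ρ), 64 in total do reach .800 at ρ = .24. But the correlation is not stated, ρ = .5 gives only .674, and the sentence limits itself to the two groups. This is a possible origin of the number, not a defence of the sentence.

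A third objection is that 70% need not apply to blood pressure reactivity. This is partly right. The 70% holds if d = .50 is measured in SDs of the change score. If d = .50 refers instead to the SD of a single measurement, with equal SDs and no group difference at rest, then the change-score effect is .50/√(2(1 − ρ)). Power at N = 100 is then .524, .697 or .975 for ρ = .25, .5 or .8; at N = 64 it is .363, .504 or .876. So any power claim for reactivity has to state its SD and its correlation.

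Finally, the paired explanation of the 64 works only near zero correlation, and the omitted words *per group* are a simpler one. The origin remains an inference, and the finding does not depend on it.

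**Conclusion.** The Aim 2 power statement is wrong as written and should be corrected. For an unadjusted, two-sided comparison of two equal groups at alpha .05 with f = .25 (d = .50), power is .504 at 64 participants in total and .697 at the planned 100; .80 needs 128, which is 28 more than will be enrolled. The index and the sidedness are assumptions, but a one-sided test and the other usual readings of .25 also miss .80 at 64. The finding covers this one sentence. It does not show that 100 is too few for the planned 2x3 ANOVA with covariates, and it does not affect the study's stated aim of estimating effect sizes.

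**What to change.** Delete the claim about 64 participants in Section VIII.C and put in its place:

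> In a simple unadjusted comparison of the two recall groups (two-sided alpha .05), 100 participants (50 per arm) give about 70% power for f = .25 (d = .50) and 80% power for f = .28 (d = .57); 80% power at f = .25 would need 128 in total (64 per group).

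If the sponsor also wants to claim power for the 2x3 ANOVA, that belongs in a separate sentence. It should rest on the condition-by-time interaction or on the change score, because randomised groups have no expected difference at rest. It should state the assumed within-person correlation and the SD to which the effect size refers.

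The cost is a change of wording and a less favourable figure for the simple comparison. No added enrolment, and no change to endpoints, procedures or analysis, is needed.
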